This document is electronically controlled. Printed copies are considered uncontrolled.

Confidential

1. Version History

Version	Summary of Changes	Author(s)/Title
1.0	
 First version 	[name], Statistician
2.0	
 Add section 9: COVID-19 related analyses Add section 10: References 	[name], Statistician
3.0	
 Changed statistical method to require that each stratum contains approximately equal number of subjects from SPYRAL DYSTAL study cohort 	[name], Statistician

2. List of Abbreviations and Definitions of Terms

Abbreviation	Definition
ABP	Ambulatory Blood Pressure
AE	Adverse Event
CIP	Clinical Investigation Plan
DBP	Diastolic Blood Pressure
eGFR	Estimated Glomerular Filtration Rate
OBP	Office Blood Pressure
SAP	Statistical Analysis Plan
SBP	Systolic Blood Pressure

3. Introduction

This document outlines the detailed statistical methods to be implemented for the data collected within the scope of the Medtronic SPYRAL DYSTAL Study: Renal denervation in the distal portion of the main renal arteries and first order branches. The objective of this single arm interventional study is to determine if renal denervation performed in the distal main and first order branch renal arteries is as effective in reducing blood pressure as the procedural approach used in the SPYRAL HTN-OFF MED clinical study. Specifically,

This document is electronically controlled. Printed copies are considered uncontrolled.

Confidential

the SAP has the following purpose: to prospectively outline the types of analyses and presentations of data that will form the basis for conclusions to be reached that will answer the trial objectives outlined in the protocol, and to explain in detail how the data will be handled and analyzed, adhering to commonly accepted standards and practices of biostatistical analysis in the medical device industry. Results obtained from the analyses outlined in this document will be the basis of the Clinical Study Report (CSR) for this trial.

4. Study Objectives

The objective of this single arm interventional study is to determine if renal denervation performed in the distal main renal arteries and branch vessels coming off the main renal artery (first order branches) is as effective as the procedural approach in the SPYRAL HTN-OFF MED clinical study.

5. Investigation Plan

The SPYRAL DYSTAL study is a multi-center, international, prospective, interventional, single arm study. Denervation will be performed using the Symplicity Spyral™ multi-electrode renal denervation catheter (Symplicity Spyral™ catheter) and the Symplicity G3™ renal denervation radio frequency (RF) generator in a hypertensive population. Subjects will be studied to assess the impact of this renal denervation approach on systolic and diastolic blood pressure. Based on the previous experience with the SPYRAL HTN-OFF MED study, it is anticipated that several subjects will no longer meet study eligibility during the screening period; therefore, approximately 350 subjects with uncontrolled hypertension will be enrolled to ensure approximately 50 hypertensive subjects will undergo the renal denervation procedure at up to 15 sites. Enrollment is expected to take approximately 12 months.

The efficacy endpoints in this study will be compared to the SPYRAL HTN-OFF MED efficacy endpoints using a propensity score stratified analysis. The SPYRAL HTN-OFF MED study was chosen because this study has the same eligibility criteria as the SPYRAL DYSTAL study, except for the anatomical exclusion criteria. The studies both evaluate blood pressure response in the absence of antihypertensive medications (Office Blood Pressure (OBP) and Ambulatory Blood Pressure Machines (ABPM)). The SPYRAL HTN-OFF MED and the SPYRAL DYSTAL studies have different procedural requirements which allows for comparison of blood pressure reductions between the two studies.

6. Determination of Sample Size

This study does not have a statistically powered hypothesis to determine if renal denervation performed in the distal main renal arteries and first order branches is as effective as the procedural approach in the SPYRAL HTN-OFF MED clinical study. The sample size of 50 subjects was chosen to provide a reasonable estimate of the efficacy of this procedural approach. In the original first phase of the SPYRAL HTN-OFF MED, only 38 subjects were sufficient in demonstrating efficacy (ASBP drop of -5.5 mmHg, with 95% CI of -9.1 to -2.0 and significant p-value of 0.003). By enrolling 50 subjects in the current study, we allow for potential missing outcomes data.

This document is electronically controlled. Printed copies are considered uncontrolled.

Confidential

7. Statistical Methods

7.1. Study Subjects

7.1.1. Disposition of Subjects

A subject disposition table will be provided for each follow-up visit containing the following information:

- The number of subjects who died or withdrew prior to each follow-up
- The number of subjects eligible for each follow-up visit
- The number of subjects completing each follow-up visit within the protocol specified window
- The number of subjects completing each follow-up outside the protocol specified window
- The number of subjects who did not complete their follow-up

7.1.2. Clinical Investigation Plan (CIP) Deviations

A study deviation is defined as an event where the investigator or site personnel did not conduct the study according to the Clinical Investigational Plan, IRB/EC, applicable laws or regulations, or the investigator Agreement. Investigators are not allowed to deviate from the protocol, except under emergency circumstances to protect the rights, safety and well-being of human subjects. Deviations shall be reported to Medtronic regardless of whether medically justifiable, pre-approved by Medtronic, or taken to protect the subject in an emergency. Deviations to protect the life or physical wellbeing of the subject in an emergency must be reported to Medtronic and the EC/IRB within five working days. Medtronic is responsible for analyzing deviations, assessing their significance, and identifying any additional corrective and/or preventive actions (e.g. amend the CIP, additional training, terminate the study, etc.). More details can be found in section 9.4 of the study protocol.

7.1.3. Analysis Sets

7.1.3.1. Intention-To-Treat (ITT) Population

All enrolled subjects are included in the intention-to-treat population. Subjects who meet the antihypertensive medication escape criteria (confirmed OSBP \geq 180 mmHg or safety reasons) will be analyzed using Last Observation Carried Forward (LOCF) for their blood pressure measurements, safety outcomes, and office and ambulatory blood pressure outcomes from procedure up to 3 months will be presented for this population.

The LOCF will be determined for the subjects who meets all following criteria:

1. Include any office or ambulatory BP values performed \leq escape date.
2. Include any office or ambulatory BP values performed \geq 30 days post procedure date.
3. Use most recent remaining greater than 30 days post-procedure measurement up to 3 months, including unscheduled BP measurements.

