In order to test the hypothesis in the SPYRAL PIVOTAL - SPYRAL HTN-OFF MED study that renal denervation decreases blood pressure and is safe when studied in the absence of antihypertensive medications, study subjects were randomized to the Denervation or Control group in a 1:1 fashion. In addition to subjects being blinded to their randomization assignment, site personnel involved in the measurement of office blood pressure were also blinded to study subjects' randomization assignment through the primary endpoint to prevent potential bias of results. Subjects were studied in the absence of antihypertensive medications to assess the impact of renal denervation on systolic blood pressure in the absence of medication.

Study enrollment was stopped for efficacy after the first interim analysis in February 2020. Data from the initial 80 patients with three months follow up from the SPYRAL HTN-OFF MED study was combined with data from the initial 251 patients with three months follow up from the SPYRAL PIVOTAL-SPYRAL HTN-OFF MED study and was presented at ACC World Congress of Cardiology in March 2020. Concurrently, an article presenting the data was published in *The Lancet*. A brief summary of the SPYRAL PIVOTAL-SPYRAL HTN-OFF MED data is provided below.

The primary endpoint, change in 24-h blood pressure at three months, was compared between groups. Drug surveillance was done to ensure patient compliance with absence of antihypertensive medication. The primary analysis was done in the intention-to-treat population. Safety events were assessed to three months.

From June 25, 2015, to Oct 15, 2019, 1519 patients were enrolled, of whom 1188 were excluded because they did not meet inclusion criteria. 166 were randomly assigned to renal denervation and 165 to the sham procedure (80 were included in the pilot and 251 in Pivotal).

There were no major safety events reported at one month. There was one major safety event in each treatment group up to three months (one admission to hospital for hypertensive crisis or emergency in the renal denervation group and one new stroke in the sham procedure group), and neither was attributed to the device or trial procedures.

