## **5.1. Duration**

Subjects will participate in the study from the time of signing consent (defined as enrollment) until study exit or the time of completion of at least 12 months of follow up post-procedure (subjects will be consented for a maximum follow-up of 5 years in case there are reasons that would require the follow up to be extended beyond the currently planned 12-months follow up).

Enrollment is expected to take approximately 12 months. Individual investigational sites may enroll up to 20% of the total study subjects. Total study duration is expected to take approximately 2.5 years.

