### 8.2. Subject Enrollment

Subjects will be pre-screened for potential enrollment in the clinical study based on prior medical history and records of office systolic blood pressure.

A subject is considered enrolled in this clinical study at the time at which the subject and investigator or authorized designee have personally signed and dated the Patient Information and Informed Consent Form. Written informed consent must be obtained prior to Screening Visit 1.

Investigational sites will maintain a subject identification log; however, this document will not be submitted to the sponsor.

It is anticipated to enroll approximately 350 subjects to reach approximately 50 renal denervation treated subjects within this study.

Each site will receive a supply of single-use catheters. A minimum of 50 single use catheters will be required to treat approximately 50 subjects. It is anticipated that a small number (<10%) of catheters will need to be replaced due to damage or contamination. Sites will be expected to return all unused study product to Medtronic.

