**Table 5: Scenarios for Subject Exit from Study**

Scenario	Follow up Required
Subject enrolled (Patient Information and Informed Consent form signed), but the procedure is never attempted	None
Subject enrolled and exits the study early due to any of the following: - death - withdrawal	Through point of death, withdrawal, or last visit completed; consent to continue to allow data collection from their medical records is required
Subject enrolled, undergoes renal denervation and completes the study requirements	Through a minimum of 12 months follow up post-procedure up to a maximum of 5 years follow up post-procedure.

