### 13.2. Analysis Sets

#### 13.2.1. *Intention-To-Treat Population*

All enrolled subjects are included in the intention-to-treat (ITT) population. Subjects who meet the anti-hypertensive medication escape criteria ( $OSBP \geq 180$  mmHg or safety reasons) will be analyzed using last observation carried forward (LOCF) for their blood pressure measurements. More details on the algorithm can be found in the table specifications document. Safety outcomes, and office and ambulatory blood pressure outcomes out to three months will be presented for this population.

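### The primary ITT set is defined as everyone who consented, so as written about 300 of 350 members would be untreated yet enter the propensity steps; separately, the modified ITT sentence is inverted

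*SAP*

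**What the plan says.** **ITT.** SAP 7.1.3.1 reads "All enrolled subjects are included in the intention-to-treat population" and Protocol 13.2.1 reads "All enrolled subjects are included in the intention-to-treat (ITT) population". Protocol 13.4 and SAP 7.7.2.1 make this the primary population for the 3-month comparison, with modified ITT and per protocol as secondary.

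**Enrollment.** Protocol 5.1 ties enrollment to consent: "Subjects will participate in the study from the time of signing consent (defined as enrollment". Protocol 8.2 says the same and adds: "It is anticipated to enroll approximately 350 subjects to reach approximately 50 renal denervation treated subjects within this study". Protocol Table 5 has a category for the remainder, "Subject enrolled (Patient Information and Informed Consent form signed), but the procedure is never attempted", and requires no follow-up for it.

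**Propensity steps.** SAP 7.7.2.1 first imputes missing covariates. It then fits a logistic model for membership of the DYSTAL cohort and scores every patient. Next it cuts the whole population into five strata with roughly equal DYSTAL numbers. Finally it combines stratum-specific ANCOVA effects with weights based on N_kD + N_kR. The comparator is the treated denervation subjects of SPYRAL HTN-OFF MED.

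**Modified ITT.** In Protocol 13.2.2 and SAP 7.1.3.2, the subject of the sentence is every enrolled subject other than those who escape, and the verb excludes them.

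**The concern.** The comparison is meant to set treated DYSTAL subjects against treated OFF MED subjects with similar baseline characteristics. Under the stated definition, the score instead separates people who consented to DYSTAL from people who were treated in OFF MED. SAP 5 says the two studies share eligibility criteria apart from anatomy. A DYSTAL subject who fails screening on Screening Visit 2 blood pressure therefore lies outside the comparator's eligible range, but would still help fit the score and place the cuts. A subject who leaves before Screening Visit 2 has no baseline blood pressure, so all four blood pressure covariates would be random draws.

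This is the primary set of an open, single-arm study. If the wording stays, either the literal rule is run, or someone decides who belongs to ITT after outcomes are known. The doubtful cases include subjects who had an angiogram but no denervation, because Protocol 9.1.5.1 completes eligibility during the angiogram.

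**Working it through.** **1. The plan's own figures.**
- Sample size (SAP 6, Protocol 13.3): n = 38, mean change -5.5, 95% CI -9.1 to -2.0. With 37 df, SE = (9.1 - 2.0)/(2 × 2.026) = 1.752 and t = 5.5/1.752 = 3.14, so p = 0.0033. This agrees with the stated 0.003. The 50 is thus argued from subjects who have an outcome.
- OFF MED (Protocol 3.1): "1519 patients were enrolled, of whom 1188 were excluded because they did not meet inclusion criteria", and "166 were randomly assigned to renal denervation and 165 to the sham procedure". 1519 - 1188 = 331 = 166 + 165. In that study too, enrolled subjects were counted before exclusions (1188/1519 = 78%), and the denervation arm was formed after them.

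**2. Make-up of ITT as written.** Inputs from Protocol 8.2: 350 enrolled, 50 treated.
- Untreated: 350 - 50 = 300, and 300/350 = 86%.
- Sensitivity: at the OFF MED yield of 331/1519 = 21.8%, treating 50 needs 50/0.218 ≈ 229 consents. Then 179/229 = 78% are untreated. The conclusion does not depend on the figure of 350.

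**3. One untreated subject followed through the steps.**

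| Step | Is the subject removed? | Reason |
|---|---|---|
| Covariate imputation (SAP 7.7.2.1) | No | Applies to missing covariates, with no treated filter |
| Propensity model (SAP 7.7.2.1) | No | Every patient is scored; the outcome is cohort membership |
| Stratum cuts (SAP 7.7.2.1) | No | Whole population, cut on DYSTAL counts |
| Weights w_k (SAP 7.7.2.1) | Unclear | N_kD is not defined; the weight option is described by total units |
| Stratum ANCOVA | Yes | No procedure date for the windows (SAP 11.2, 11.3), no 3-month value, no outcome imputation (SAP 7.3) |

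The KEY=TREATED option does not act as a filter. The SAP explains it as balancing numbers from the DYSTAL cohort, not numbers who received denervation.

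**4. Counts.** The comparator is 166 from Protocol 3.1. The size of the secondary cohort in SAP Table 1 is not given, so 250 is used as an assumed upper case.

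| Quantity | As written | Treated only |
|---|---|---|
| DYSTAL per stratum | 350/5 = 70 | 50/5 = 10 |
| Treated DYSTAL per stratum | 10 on average, not guaranteed | 10 |
| DYSTAL share of scored subjects, 166 comparators | 350/516 = 68% | 50/216 = 23% |
| Same, 250 comparators (assumed) | 350/600 = 58% | 50/300 = 17% |

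If N_kD counts set members, untreated subjects make up 300/516 = 58% of the weighting units, or 300/600 = 50% with 250 comparators.

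**5. Modified ITT.** Let E be enrolled subjects and X those who escape. The sentence excludes E minus X, which leaves X. Per-protocol criterion 4 (Protocol 13.2.3, SAP 7.1.3.3) excludes X, so the reverse was evidently meant.

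**The case against.** The strongest reply is that a treated set was plainly intended. SAP 6 says "By enrolling 50 subjects in the current study, we allow for potential missing outcomes data", which uses enrollment to mean treatment. SAP 7.1.3.1 counts outcomes, and the days for carrying values forward, from the procedure. SAP 11.2 and 11.3 define windows from the procedure date. SAP 7.7.3 presents ablation data for ITT. This stands as evidence of intent, and it means that a reader should not infer a deliberate plan to model screen failures. It does not settle the definition. Only the per-protocol set is limited to treated subjects, and no section says the same for ITT or places angiogram-only subjects.

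A reader might go further and infer that the 3-month blood pressure difference is materially biased, or that some strata could not be estimated. The documents do not support either. The effect depends on how screen failures differ from treated subjects and on how many have missing covariates, and neither is given. If screen failures resemble treated subjects, the effect could be negligible.

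A reader might also infer that the safety rates are diluted by untreated subjects, since safety uses ITT too. The denominator rule in SAP 7.7.1 requires an adjudicated event or a last contact beyond the lower visit window, which removes most screen failures.

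Finally, there is no powered hypothesis (Protocol 13.3, SAP 7.4), and the modified ITT slip touches only a secondary analysis whose intent is clear.

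**Conclusion.** Wrong as written, and worth fixing before the analysis. The primary efficacy set takes in every consented subject, of whom about 86% would be untreated on the plan's own numbers (78% at the OFF MED yield). They do not contribute outcomes. As written they do contribute to the covariate imputation, the score and the cuts, and to the weights as well if N_kD counts set members. The comparator has no such members.

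The 300 of 350 and the 70 against 10 per stratum rest only on the documents. The shares of scored and weighted units also rest on the comparator size, which is known only in part. No direction or size of bias in the blood pressure difference is claimed. The modified ITT inversion needs no assumption, but matters less.

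**What to change.** - **Protocol 13.2.1 and SAP 7.1.3.1:** define the efficacy ITT set by the denervation procedure, for example enrolled subjects in whom denervation was begun. State explicitly whether subjects who had only the angiogram are in or out. Keep the definition consistent with the treated OFF MED comparator already named in Protocol 13.4 and SAP 7.7.2.1.
- **SAP 7.7.2.1:** state that only this set supplies the DYSTAL subjects for covariate imputation, propensity model, strata and weights, and define N_kD accordingly.
- **Protocol 13.2.2 and SAP 7.1.3.2:** replace the sentence with *ITT subjects, excluding those who meet the escape criteria*.

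The cost is a few sentences in two documents. No new data, visits or analyses are needed.

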### ***9.1.9. Anti-hypertensive medication escape criteria***

In the event a subject's office SBP  $\geq$ 180 mmHg, or there is a safety concern, from discharge up to and including the 3-month visit, the subject will be seen a second time within 72 hours for a repeat office BP. If the subject's office SBP remains  $\geq$ 180 mmHg, the subject will be put back on an antihypertensive medication regimen per the investigator's discretion. All efforts should be made to obtain an ABPM and Chem-7 panel, and urine and blood for antihypertensive drug testing, prior to the subject being put back on medications. If the subject already started medications, the subject and investigator should consider if it is safe to take the subject off medications for at least two weeks prior to the 3M visit in order to obtain the requirements at the 3-month visit to ensure endpoint data is collected. The subject will be exited from the off medications portion of the study and will be followed according to **Table 4**. If the subject's office SBP < 180 mmHg, the subject will continue to be followed per **Table 3**. At any time while the subject is not taking antihypertensive medications, either the subject or the investigator may restart antihypertensive medications if there is a safety concern and the subject will be followed according to **Table 4**. All blood pressures must be taken according to the guidelines in **Appendix 16.5** with the exception of needing to be completed by 10:30 am. Visits for monitoring the subject's BP for these purposes must be documented on the CRF.

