7.3. Handling of Missing Data and Dropouts

No imputation of missing data will be performed.

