7.7.2.1. Efficacy Objectives Evaluation at 3 Months

Since subjects in the two comparative groups were not directly randomized, a direct comparison may not be appropriate. The efficacy endpoints at 3-months will be compared to the RDN treated subjects from the SPYRAL HTN-OFF MED clinical study using propensity score stratification (subclassification) adjustment. A propensity score will be estimated for each patient from a multivariable logistic regression model, which is the probability that the patient is in DYSTAL cohort. In this model, the DYSTAL cohort (binary variable) is the outcome variable, and the following covariates will be considered as independent variables for propensity score analysis model: baseline Office SBP and DBP as well as the SBP and DBP measured by 24-hour ABPM (continuous), age (continuous), gender (dichotomous), BMI (continuous), diabetes (dichotomous).

The missing values in the covariates will be imputed first before the propensity score stratification. For continuous variables, the missing values will be imputed by CALL STREAMINIT(seed) and RAND('NORMAL', MU, S²), where MU denotes the sample mean of the specific continuous variable, S denotes the sample standard deviation. If the imputed value is above the maximum value of that variable, the maximum value will be used as the imputed value; if the imputed value is below the minimum value of the variable, the minimum value will be used as the imputed value. For binary categorical variables, the missing values will be imputed as RANBIN(seed, 1, p), where p denotes the observed proportion of the specific binary baseline variable in each arm. The seed will be set as 121919, applied for both continuous and binary variable imputations.

After propensity scores are estimated, the entire population will be divided into 5 strata using the quintiles of the ordered propensity scores, with approximate equal number of subjects from Dystal study cohort in each stratum. This will be done using PROC PSMATCH in SAS 9.4, specifying the option KEY=TREATED in STRATA statement to require that each stratum contain approximately equal number of subjects from Dystal cohort. The option STRATUMWGT=TOTAL in STRATA statement, which uses the proportional size (number of total units in the stratum divided by the total number of units) of the stratum, will provide the average treatment effect weight for each observation.

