After stratification, analysis of covariance (ANCOVA) models adjusting for the baseline BP measurements will also be presented for each propensity score stratum to obtain the strata-specific treatment effect, which can be combined to yield an overall treatment effect (DYSTAL minus SPYRAL HTN-OFF MED RDN arm). The overall treatment effect together with two-sided 95% confidence interval will be calculated as follows:

$$(\mu_D - \mu_R) \pm 1.96 \times \text{SE}(\mu_D - \mu_R),$$

where $\mu_D - \mu_R$ is the weighted mean of overall treatment effect given by

This document is electronically controlled. Printed copies are considered uncontrolled.

Confidential

$$\mu_D - \mu_R = \sum_{k=1}^5 w_k (\mu_{kD} - \mu_{kR}),$$

with k the number of stratum ($k = 1, 2, 3, 4, 5$), and w_k as the weight for k^{th} stratum defined by

$$w_k = \frac{N_{kD} + N_{kR}}{\sum_{k=1}^5 (N_{kD} + N_{kR})}$$

Additionally, $\mu_{kD} - \mu_{kR}$ is the mean of treatment effect in k^{th} stratum from an ANCOVA adjusted model, and $SE(\mu_D - \mu_R)$ is the weighted standard error of overall treatment effect

$$SE(\mu_D - \mu_R) = \sqrt{\sum_{k=1}^5 w_k^2 * SE^2(\mu_{kD} - \mu_{kR})},$$

where $SE(\mu_{kD} - \mu_{kR})$ is the standard error of treatment effect in k^{th} stratum.

The ITT population will be the primary analysis population, and secondary analyses will be performed on the modified ITT and per protocol populations in 7.1.3.2 and 7.1.3.3.

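### A subject who restarts drugs before day 30 has no blood pressure value that the SAP's LOCF rule can carry forward, and the SAP states no fallback

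*SAP*

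**What the plan says.** SAP 7.1.3.1 states that ITT subjects who meet the escape criteria "will be analyzed using Last Observation Carried Forward (LOCF) for their blood pressure measurements". Three items define the carried value:

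- Item 1: the value is dated no later than the escape date.
- Item 2: it is dated 30 or more days after the procedure.
- Item 3, the selection step: "Use most recent remaining greater than 30 days post-procedure measurement up to 3 months, including unscheduled BP measurements".

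Protocol 9.1.9 sets the period in which a high office reading triggers escape: "from discharge up to and including the 3-month visit". It asks for a repeat reading within 72 hours, and drugs restart if SBP is still 180 mmHg or above. It also provides that "either the subject or the investigator may restart antihypertensive medications if there is a safety concern". On 24-hour pressure before restart it says "All efforts should be made to obtain an ABPM", which is a best-effort request. Protocol Table 3 schedules ABPM at SV2 and 3 months with nothing between, and Table 4, the schedule for escapers, lists none.

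SAP 7.3 reads in full: "No imputation of missing data will be performed". SAP 7.7.2.1 adds: "The ITT population will be the primary analysis population". Protocol 13.2.1 refers readers to a table specifications document for more on the LOCF algorithm. That document is not among those available, and SAP 7.1.3.1 does not cite it.

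**The concern.** Items 1 and 2 cannot both be met by someone who escapes before day 30. The SAP says such a subject will be analysed by LOCF, yet leaves nothing to carry and gives no substitute.

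This matters because ITT is the population in which escapers are meant to count. The per-protocol set excludes them and, by evident intent, so does the modified ITT set. A confirmed-BP escaper had office SBP below 180 mmHg at SV2 (an entry criterion) and 180 or above at escape, so the off-drug office change is a rise and the subject is not below 140 mmHg. Losing that subject makes the DYSTAL office SBP change and target rate look better. A subject who restarts for another safety reason need not be worse than baseline, so no direction can be given for that group.

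The SAP also does not say that the LOCF rule applies to the OFF MED RDN subjects, and the fairness of the 3-month comparison depends on that.

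**Working it through.** **1. Escape days with no eligible value.** Let d be the day of a BP reading and E the escape day, both counted from the procedure. Items 1 and 2 need 30 ≤ d ≤ E, which is empty for E < 30. Item 3 needs d > 30, so it is also empty at E = 30.

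| Escape day E | Eligible days, items 1-2 | Eligible days, items 1-3 |
|---|---|---|
| 14 | 0 | 0 |
| 29 | 0 | 0 |
| 30 | 1 | 0 |
| 31 | 2 | 1 |
| 37 | 8 | 7 |

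**2. Visits affected (windows from Protocol Table 3).** I take the escape date as the date of the confirming reading, or of a discretionary restart; the SAP does not define it.

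- 2-week visit: 14 ± 3 = days 11-17. A repeat within 72 hours falls by day 17 + 3 = 20, so every such escape is empty.
- 1-month visit: 30 ± 7 = days 23-37 (15 days). A first high reading on day v is repeated by day v + 3. Under item 2 the set is certainly empty if v + 3 < 30, that is v ≤ 26: days 23-26, or 4 of 15.
- Days 27-29: the repeat may fall on days 30-32, and item 3 accepts unscheduled readings, so the result depends on when the repeat is taken. (Under item 3's stricter bound, day 27 joins the certain group, since 27 + 3 = 30.)

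**3. 24-hour BP.** With no ABPM scheduled between SV2 and 3 months, an escaper after day 30 has an eligible value only if an ABPM was obtained before drugs restarted.

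**4. SD, from the plan's own figure (SAP 6: n = 38, -5.5 mmHg, 95% CI -9.1 to -2.0, p = 0.003).** Half-width = (9.1 - 2.0)/2 = 3.55. With t(37) = 2.026, SE = 3.55/2.026 = 1.752 and SD = 1.752 × √38 = 10.8. The recomputed p is 0.0033, which agrees with the plan.

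**5. Shift in the raw DYSTAL mean, 24-hour SBP.** Assume k of 50 are dropped, their true change was 0, and the rest average -5.5. The mean with them is -5.5 × (50 - k)/50; without them it is -5.5. Shift = 5.5 × k/50.

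The SE of the difference against 166 OFF MED RDN subjects (Protocol 3.1) is 10.8 × √(1/50 + 1/166) = 1.74. SAP Table 1 adds a secondary cohort of unstated size, but the SE cannot fall below 10.8/√50 = 1.53.

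| k (assumed) | Shift, mmHg | Shift / 1.74 |
|---|---|---|
| 1 | 0.11 | 0.06 |
| 3 | 0.33 | 0.19 |
| 5 | 0.55 | 0.32 |

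**6. Planned stratified estimate.** SAP 7.7.2.1 forms five strata "with approximate equal number of subjects from Dystal study cohort in each stratum", so about 10 each, weighted by total stratum size. Before ANCOVA adjustment, one lost subject shifts the result by w × 5.5/10: 0.11 mmHg at w = 0.2 and 0.22 at w = 0.4.

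**7. Between-study difference.** If early escapers are dropped in both cohorts, bias = 5.5 × (early-escape proportion in DYSTAL minus that in OFF MED): 0 when equal, 0.11 mmHg for a gap of 2 percentage points, 0.55 for 10.

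**8. Office SBP below 140.** Assume 15/50 = 30.0% at target. Dropping one non-responder gives 15/49 = 30.6%; dropping five gives 15/45 = 33.3%.

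**The case against.** The strongest reply is that the protocol names a place for LOCF detail, the table specifications document, and it may hold a fallback. That stands as a limit: the documents show that the SAP is silent, not that no rule exists anywhere. But the SAP says its purpose is to set out data handling in detail, and this section neither cites that document nor resolves the empty set.

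A second reply is that a default can be read from the text: LOCF applies only to those with a qualifying value, nothing is imputed, so the rest are missing. I accept that as the most natural reading. It is also the consequence at issue, since the primary population then loses the subjects it was meant to keep. A deliberate 30-day floor would be defensible, but its effect on early escapers would still need stating.

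It is also fair to say that the consequence is small, that there is no powered hypothesis, and that Protocol 13.7 requires the number analysed to be reported, so a loss would show as a count.

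A reader might infer more than the documents support:

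- *That early escapers re-enter with an on-drug 3-month office value through SAP Appendix II (days 61-135).* On the assumptions of step 8, that would lift the target rate to 16/50 = 32% or 20/50 = 40%. But SAP 7.1.3.1 assigns escapers to LOCF and Protocol 9.1.9 exits them from the off-medication portion, so this is the weaker reading. A 3-month value taken after the re-withdrawal that Protocol 9.1.9 asks sites to consider would be off drug and would not flatter the result.
- *That 7 of the 15 days of the 1-month window (days 23-29) are always lost.* That holds for a same-day discretionary restart, not for confirmed-BP escape, because of the 72-hour repeat.
- *That the clash between items 2 and 3 at day 30 is a serious fault.* It affects only an escaper whose sole eligible value falls exactly on day 30.

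**Conclusion.** The gap is real and minor. As written, SAP 7.1.3.1 leaves every escaper before day 30 without an eligible office or 24-hour value, and later escapers without a 24-hour value unless an ABPM preceded restart. With SAP 7.3, the likely result is that they drop out of the primary 3-month efficacy analysis.

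For confirmed-BP escapers the direction on the two office SBP endpoints follows from the entry and escape thresholds. The mmHg figures are for 24-hour SBP and rest wholly on assumptions: 1 to 5 early escapers, zero change in them, and -5.5 mmHg in the rest. The documents give no escape rate or timing, so the true size is unknown.

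It would be wrong to infer that the comparison with OFF MED is biased by a known amount. The bias vanishes if early-escape rates and handling match, and no margin or success rule is stated that a shift of this size could reverse.

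**What to change.** Change the SAP only:

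- In 7.1.3.1, align item 3 with item 2 (at least 30 days).
- Add that an escape subject with no eligible value of a given measure (office or 24-hour) under items 1-3 has the SV2 baseline carried forward: change of zero, and not at target for office SBP below 140.
- Add that values taken on restarted drugs are not used as 3-month off-drug results.
- State that the same rule applies to the OFF MED RDN subjects.
- In 7.3, add an exception for 7.1.3.1.
- Report the number using the fallback in each cohort.
- As a sensitivity analysis, use the last off-drug value on or before escape regardless of the 30-day floor, or an off-drug 3-month value after re-withdrawal where one exists.

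If the table specifications document already holds a rule, bring it into the SAP and apply it to both cohorts.

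The cost is a few sentences and a re-run of the rule on the OFF MED RDN data. No protocol amendment is needed, because Protocol 13.7 leaves room for imputation that is specified elsewhere. Baseline carry-forward is crude: it understates the office rise in confirmed-BP escapers and makes the estimate slightly less favourable.
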